- s. If a subject discontinues study treatment or withdraws from the study, every attempt should be made to complete the early termination (ET) visit within 2 weeks of the last dose of study drug. Ultrasound, Bayley-III, and motor milestone checklist will not be performed at the ET visit if the assessment was conducted within 1 month of termination.
- t. Optional assessment can be performed at a different time-point if total blood volume at week 16 may exceed maximum allowable volume.

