### **7.5.2.1 Primary Efficacy Measure: Urinary GAG Excretion**

Clinical evidence for the use of uGAG as a relevant primary endpoint is based on nonclinical research work over 20 years, clinical disease survey studies, and Phase 3 controlled studies in MPS 1, 2 and 6 patients using other ERTs. The results demonstrate a direct relationship between disease severity and clinical outcomes with uGAG levels. The studies also demonstrate the sensitivity of uGAG to differences in clinical effect within the therapeutic range of doses and verified the sustained long-term effects of the ERT. The overall summary of these data show that uGAG reductions above a threshold of >50% are associated with clinically meaningful changes in clinical parameters in all three MPS ERT programs.

First morning void urine will be evaluated for uGAG at the time points listed in the schedule of events ([Table 2.1](#)). Urine samples will be collected once during Screening Period and on two separate days during the Baseline Period (Week 0). Urine samples must be collected from first morning voids to assure the urine is adequately concentrated. Samples will be evaluated for uGAG concentration and normalized to urinary creatinine concentration. Refer to the Laboratory Manual for details on sample collection and processing requirements.

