### **7.6.2 Subject Information**

Subject disposition summaries will include the number of subjects, the number of subjects receiving study medication, the number of subjects completing the study, and the reasons for discontinuation. Demographic variables include age, sex, and race.

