### 3.1 Overall Study Design and Plan

[figure not shown]
UX003-CL203 is an open-label, multicenter, Phase 2 study to assess the safety and efficacy of UX003 in pediatric MPS 7 subjects less than 5 years of age. UX003 is a formulation of recombinant human rhGUS, a human enzyme produced by recombinant DNA methods that is intended as an enzyme replacement therapy (ERT) for MPS 7. The study seeks to enroll up to 15 subjects less than 5 years of age at the time of signing informed consent, and will attempt to include approximately 5 infants with hydrops fetalis if possible. Subjects less than 5 years of age with prior exposure to UX003 treatment under an emergency IND may also be enrolled at the discretion of the Ultragenyx. The inclusion criteria are structured to enroll subjects with a confirmed diagnosis of MPS 7. To enroll subjects most likely to benefit from treatment and demonstrate safety and effectiveness of UX003, MPS 7 patients who have

undergone successful bone marrow or stem cell transplantation will be excluded from the study. Subjects who withdraw or are removed from the study after receiving study drug may be replaced on a case-by-case basis, at the discretion of Ultragenyx.

Subjects will receive UX003 via intravenous (IV) infusion at a dose of 4 mg/kg every other week (QOW). Subjects who complete the 48-week study may choose to continue UX003 treatment in the Continuation Period up to 240 weeks, or until the subject withdraws consent, the subject is discontinued from the study at the discretion of the Investigator or Ultragenyx, the study is terminated, or UX003 becomes commercially available.

Figure 3.1 provides a schematic of the study design.

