### 8.2 Subject Disposition

The subjects in the full analysis set will be listed. Date of informed consent, the reason for treatment discontinuation and study discontinuation will be displayed.

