### 8.3 Demographics and Other Baseline Characteristics

Demographic parameters (e.g., age, sex, race and ethnicity) and other baseline characteristics (i.e., initial diagnosis, height and weight) assessed at baseline will be summarized and listed.

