## 8.7 Efficacy Analyses

### 8.7.1 Primary Efficacy Endpoint

The primary efficacy analysis will evaluate the mean percent change in uGAG excretion from baseline at week 48 using the generalized estimating equation (GEE) analysis method. The model will include baseline and visit (up to week 48) as a categorical variable. The covariance structure within subjects will be assumed to be exchangeable. For subject(s) previously treated with UX003 under an emergency IND, percent change from initial baseline will be calculated.

In addition, the change and percentage change from baseline, fold increase in uGAG excretion and number of uGAG responders (defined as  $\geq 50\%$  decrease in uGAG excretion from baseline) will be presented by visit.

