## 9 CHANGES TO ANALYSES SPECIFIED IN PROTOCOL

There are no major changes to the analyses specified in the Protocol Amendment 1 (dated 05 October 2015)

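### Does the by-visit uGAG responder count, with disposition given only as a listing, hide subjects who die or leave the study?

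*SAP*

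**What the plan says.** **Responders.** SAP 8.7.1 sets the primary analysis as a GEE model for percent change in uGAG to Week 48. It then adds, by visit, "In addition, the change and percentage change from baseline, fold increase in uGAG excretion and number of uGAG responders", a responder being a subject whose uGAG has fallen by at least half. That section gives no denominator and no rule for death.

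**General rules.** SAP 8.1 bases all analyses on the full analysis set, asks for counts and percentages for categorical variables, and sends all raw and derived data to listings or graphs because the sample is small. SAP 7.1 leaves missing values missing. SAP 7.3 maps end-of-treatment visits to the nearest scheduled visit when that one is missing.

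**Disposition.** Protocol 7.6.2 says: "Subject disposition summaries will include the number of subjects, the number of subjects receiving study medication, the number of subjects completing the study", together with reasons for discontinuation. SAP 8.2 says: "The subjects in the full analysis set will be listed", with the consent date and reasons for stopping shown. SAP 9 states: "There are no major changes to the analyses specified in the Protocol Amendment 1".

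**Replacement.** SAP 3.1: "Subjects who withdraw or are removed from the study after receiving study drug may be replaced on a case-by-case basis".

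**The concern.** Losses are foreseeable. Both documents seek about 5 infants with hydrops fetalis among about 15 subjects, and the protocol's exclusion criteria acknowledge high mortality in that group. The early-termination rule in the schedule of events ("every attempt should be made to complete the early termination (ET) visit within 2 weeks of the last dose of study drug") helps only children who stop alive. A child who dies leaves no such visit to map.

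The responder figure also carries weight, because Protocol 7.5.2.1 says that "uGAG reductions above a threshold of >50% are associated with clinically meaningful changes in clinical parameters in all three MPS ERT programs". A Week 48 figure taken only from children still under observation could look better than the experience of everyone treated, and replacement could bring the observed number back to about 15. If disposition is only listed, no table has to place the losses beside the result. SAP 8.3, by contrast, says that baseline data "assessed at baseline will be summarized and listed", so the SAP appears to distinguish the two outputs, and SAP 9 records no departure from the protocol. Nothing in the uGAG output has to identify the hydropic infants.

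**Working it through.** The plan has no figure to reproduce: the sample size rests on finding patients, and the documents give no dropout rate or expected responder rate. The check is whether losses stay visible under the rules as written, and what the unstated denominator can change.

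**1. Size of the denominator effect.** Inputs: N = 15 treated (Protocol 7.6.1, SAP 3.2). Losses L and responders r are assumed. Observed-case rate = r/(15 − L). Full-set rate with losses counted as non-responders = r/15. Gap = rL/[15(15 − L)]. Intervals are exact (Clopper-Pearson) 95%.

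| L | r | Observed | Full set | Gap (points) |
|---|---|---|---|---|
| 1 | 11 | 11/14 = 79% (49–95) | 11/15 = 73% (45–92) | 11/210 = 5.2 |
| 3 | 10 | 10/12 = 83% (52–98) | 10/15 = 67% (38–88) | 30/180 = 16.7 |
| 5 | 8 | 8/10 = 80% (44–97) | 8/15 = 53% (27–79) | 40/150 = 26.7 |

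With L = 0 the two rates agree. In every row the count, which is what SAP 8.7.1 names, is the same on both bases. Neither reading counts a child without a value as a responder.

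**2. Can the reader tell which denominator was used?** SAP 8.1 requires the percentage, so N = count / percentage. Observed: 11/0.79 = 13.9, 10/0.83 = 12.0, 8/0.80 = 10. Full set: 11/0.73 = 15.1, 10/0.67 = 14.9, 8/0.53 = 15.1. Each rounds to the right N. This fails only when there are no responders.

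**3. Replacement.** Suppose all 5 lost subjects are replaced and 12 of the 15 observed respond: 12/15 = 80% (52–96) observed, 12/20 = 60% (36–81) on the full set. The observed N then looks complete. However, the replacement rule applies to subjects who have received study drug. They meet the full-analysis-set definition in SAP 6.1 and stay in the SAP 8.2 listing, which would have 20 rows. Five replacements are also hard to credit when the protocol puts known cases worldwide below 100.

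**4. Where a death or withdrawal appears.**

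| Output | What it shows |
|---|---|
| SAP 8.2 | Every treated subject, with reasons for stopping treatment and study |
| SAP 8.8.1 | Listings of deaths and of AEs leading to discontinuation; summary of SAEs (death is a serious outcome in Protocol 8.5.1) |
| SAP 8.6 | Number of infusions, cumulative dose, duration of exposure |
| SAP 8.1 | All raw and derived data, so each child's uGAG series and where it ends |

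Hydrops status is not a named variable, but SAP 8.3 summarises and lists initial diagnosis, and SAP 8.4 summarises medical history, in which Protocol 7.5.4.1 collects diagnoses.

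**5. Effect on the primary result.** The GEE model is specified separately from the responder display, and neither the responder denominator nor the form of the disposition output enters it. Protocol 7.6.4 names no responder endpoint, and no test of responders is planned.

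**The case for a change.** The strongest argument for a change needs no assumed numbers. The protocol promises counts, the SAP promises a listing, the SAP uses both terms where it means both, and its section on changes does not mention the difference. The listing also covers only treated subjects, so a child enrolled but never dosed falls outside it, although Protocol 7.6.2 counts subjects and treated subjects separately. The SAP is where missing-data rules belong, and it has none for death. The remedy would be a sentence and a small table.

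Much of this is accurate as description. The responder denominator is not named, and the number completing is not a required count in SAP 8.2. The inference that losses are concealed does not stand. Protocol 7.6 calls its statistical text a guide and leaves detail to the SAP. SAP 9 denies only major changes, and showing about 15 subjects individually is not clearly one. SAP 9 also refers to Amendment 1, which is not the version supplied, and Amendment 2's summary covers major changes only, so its silence on disposition settles little. The listing's wording need not exclude counts either: SAP 8.7.3 uses the same verb, displayed, for a percent change reported beside by-visit summaries, and a reason for discontinuation is a categorical variable under SAP 8.1. An undosed child has no post-treatment uGAG and cannot affect the responder figure.

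The further additions are matters of preference. Counting missing as non-response mixes survival with a biomarker. A hydrops split would describe about 5 children in a trial that plans no subgroup analysis.

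**Conclusion.** No change is needed. Two details are left unstated: the base of the responder percentage, including how deaths count, and the disposition counts that Protocol 7.6.2 mentions. Any analyst reporting about 15 children would show responders as n/N by visit and count completers and discontinuations by reason. The outputs already required hold the data to do so.

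The gap between the two possible percentages is nil with no losses and reaches 26.7 points if 5 of 15 are lost with 8 responders. Those losses and responder numbers are assumptions, as is the replacement scenario; the documents support none of them with a rate. Even in the extreme case the responder count is unchanged and the denominator or the number treated can be read from required output. Followed as written, the plan produces no wrong result or conclusion.

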### 8.7.2 Secondary Efficacy Endpoints

Change from baseline in anthropometric measurements will be summarized by visit, and for all subjects (including subject(s) previously treated with UX003 under an emergency IND), the last non-missing study assessment prior to the first dose in this study will be used as baseline.

All anthropometric measurements with z scores and percentiles will be listed. Growth velocity will be presented for pre-treatment and post-treatment periods, and for the subject(s) previously treated with UX003 under an emergency IND the growth velocity will be calculated for pre initial UX003 treatment and post initial UX003 treatment.

The change from baseline in liver and spleen size will be summarized by visit.

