#### **Secondary Efficacy Variables:**

- Growth will be assessed by anthropometric measurements including standing height (length or sitting height as applicable), head circumference, and weight. Growth velocity will be calculated and compared with pre-treatment growth velocity when available and published normative data for age and gender.
- Hepatosplenomegaly: The volume of the liver and spleen will be determined using ultrasound. If an ultrasound is not possible, the liver and spleen should be assessed by physical exam. The volume of liver and spleen will be compared to baseline and to normal values if available. Ascites will also be assessed.

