#### **Tertiary Efficacy Variables:**

- Additional GAG measures including serum GAG and supplementary uGAG assays
- Clinical Global Impression Scale: Physicians caring for each subject will provide a global assessment of change from baseline or change from identification of a new finding using a seven point scale ranging from -3 (severe worsening) to +3 (significant improvement). The Clinical Global Impression (CGI) scale will be supported by reported changes in a list of disease-specific abnormalities projected to respond to treatment.
- Functional Development will be assessed by the Bayley Scales of Infant and Toddler Development® – Third Edition (Bayley-III).
- Motor Functioning will be assessed by a motor development milestone checklist.
- Cardiac Ventricular Mass: Ventricular mass will be assessed by echocardiogram (ECHO) and scored as a z-score relative to normal ventricular mass. Valvular and cardiac function may also be evaluated.
- Pulmonary Function: Pulse oximetry will be used to assess problems in adequate respiration; resting O2 saturation will be measured while the subject is breathing room air.
- Biochemical Markers of Bone Turnover (BTMs): Levels of serum markers of bone formation and bone resorption will be measured including procollagen type 1 N-propeptide (P1NP), carboxy-terminal cross-linked telopeptide of type I collagen (CTX-I), bone-specific alkaline phosphatase (BALP), and vitamin D.

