#### **7.5.2.2.2 Hepatosplenomegaly**

The volume of the liver and spleen will be determined using ultrasound and compared with normal values for age and gender if available; ascites will also be assessed. Ultrasounds will be conducted at the Baseline (Week 0) and Week 12, 24, and 48 (or Early Termination) study visits. During the Continuation Period, an ultrasound of the liver and spleen will be performed annually (every 48 weeks). If an ultrasound cannot be performed, liver and spleen size may be assessed qualitatively by physical exam. Ultrasound will not be performed at the ET visit if the assessment was conducted within 1 month of termination.

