#### **7.5.2.3.5 Cardiac Ventricular Mass**

Ventricular mass will be assessed by echocardiogram (ECHO) and scored as a z-score relative to normal ventricular mass. Valvular and cardiac function may also be evaluated. An ECHO performed within three months prior to the Baseline visit may be used for the study baseline ECHO provided cardiac ventricular mass can be calculated. ECHO will be performed at the Baseline (Week 0) and Week 48 (or Early Termination) study visits. During the Continuation Period, ECHO will be assessed annually (every 48 weeks).

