### 4.2 Secondary Efficacy Variables

- Growth will be assessed by anthropometric measurements including standing height (length or sitting height as applicable), head circumference, and weight. Growth velocity will be calculated and compared with pre-treatment growth velocity when available and published normative data for age and gender.
- Hepatosplenomegaly: The volume of the liver and spleen will be determined using ultrasound. If an ultrasound is not possible, the liver and spleen should be assessed by physical exam. Ascites will also be assessed.

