### 4.3 Tertiary Efficacy Variables

- Additional GAG measures including serum GAG and supplementary uGAG assays
- Clinical Global Impression Scale: Physicians caring for each subject will provide a global assessment of change using a seven point scale ranging from -3 (severe worsening) to +3 (significant improvement). The Clinical Global Impression (CGI) scale will be supported by reported changes in a list of disease-specific abnormalities projected to respond to treatment.
- Functional Development will be assessed by the Bayley Scales of Infant and Toddler Development® – Third Edition (Bayley-III).
- Motor Functioning will be assessed by a gross motor development milestone checklist.
- Cardiac Ventricular Mass: Ventricular mass will be assessed by echocardiogram (ECHO). Valvular and cardiac function may also be evaluated.
- Pulmonary Function: Pulse oximetry will be used to assess respiratory difficulties; resting O2 saturation will be measured while the subject is breathing room air.
- Biochemical Markers of Bone Turnover (BTMs): Levels of serum markers of bone formation and bone resorption will be measured.

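### SAP 8.7.2 reports liver and spleen size only as change from baseline and omits the protocol's conditional comparison with normal values, so organ growth and drug effect are mixed in children under 5

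*SAP*

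**What the plan says.** Liver and spleen. The protocol synopsis, under the secondary efficacy variables, states: "The volume of liver and spleen will be compared to baseline and to normal values if available". Protocol 7.5.2.2.2 says that ultrasound volume is to be "compared with normal values for age and gender if available". It also provides a fallback: "If an ultrasound cannot be performed, liver and spleen size may be assessed qualitatively by physical exam".

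SAP 4.2 keeps the ultrasound, physical-exam and ascites statements, but the comparison sentence that stands between the last two in the synopsis is absent: "the liver and spleen should be assessed by physical exam. Ascites will also be assessed". The analysis in SAP 8.7.2 is a single sentence: "The change from baseline in liver and spleen size will be summarized by visit". It names no normal value, age or sex reference, or body-size scale.

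Ventricular mass. The protocol synopsis states: "Ventricular mass will be assessed by echocardiogram (ECHO) and scored as a z-score relative to normal ventricular mass". Protocol 7.5.2.3.5 repeats this without condition. SAP 4.3 reads: "Ventricular mass will be assessed by echocardiogram (ECHO). Valvular and cardiac function may also be evaluated". SAP 8.7.3 lists cardiac ventricular mass among variables summarised as change from baseline and does not state the scale.

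SAP 9 reports no major changes to the analyses in Protocol Amendment 1 and mentions neither item.

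**The concern.** Subjects are under 5 at consent and all receive UX003. Ultrasound is done at Weeks 0, 12, 24 and 48 and then every 48 weeks, with treatment possible to Week 240. A healthy child's liver and spleen grow over such periods. With no control arm to show what growth alone would do, a change in raw volume cannot separate growth from treatment. An organ that is shrinking relative to normal for age may show little raw change, or even a rise, and a reader could take that as lack of effect. An external or body-size scale is the practical way to tell the two apart. The protocol provides for the first of these, and the SAP does not.

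**Working it through.** **Text check.** The SAP uses normative scales where it intends them. SAP 4.2 keeps published normative data for growth in the bullet above hepatosplenomegaly, SAP 5.3 names the CDC charts for anthropometric z-scores, and SAP 5.2 relates uGAG to its upper normal limit. Nothing equivalent is given for organ volume, so SAP 8.7.2 followed as written yields raw change only.

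**Arithmetic.** The plan gives no figure to reproduce. What follows is illustrative, and every input is an assumption. Let g be the growth of the normal organ volume between baseline and the visit, and r the true fall in the organ's multiple of normal. Then

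raw change = (1 + g)(1 - r) - 1, which is zero at g = r/(1 - r).

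Example: r = 20% and g = 30% give 1.30 × 0.80 - 1 = +4%.

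| g | r = 10% | r = 20% | r = 30% |
|---|---|---|---|
| 10% | -1% | -12% | -23% |
| 20% | +8% | -4% | -16% |
| 30% | +17% | +4% | -9% |
| 50% | +35% | +20% | +5% |
| g at which raw change is zero | 11.1% | 25.0% | 42.9% |

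The direction is consistent: for any positive g, the raw change understates the fall relative to normal. Its sign reverses only when g passes the value in the last row.

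**The remedy has its own errors, which need the same check.**

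- *Age norms and slow growth.* Suppose there is no drug effect and the organ grows at half the normal rate. The multiple of normal changes by (1 + 0.5g)/(1 + g) - 1. For g = 10%, 20%, 30% and 50% this is -4.5%, -8.3%, -11.5% and -16.7%, while raw size rises by 5%, 10%, 15% and 25%. The age-normed value would look like benefit. Protocol 5 and 5.1 list short stature as a feature of MPS 7, so this is not remote.
- *Weight as the adjuster.* With organ volume unchanged, the per-kg value changes by 1/(1 + w) - 1 for a weight change w. A 20% loss of fluid weight gives 1/0.80 - 1 = +25%, and a 20% gain gives 1/1.20 - 1 = -16.7%. The trial hopes to enrol about 5 infants with hydrops fetalis, so fluid-driven weight change is likely in some subjects.

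No single scale is clean. That is the reason to report a scaled value beside the raw one and not in its place.

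**The case against.** The strongest reply is that the SAP does follow the protocol's statistical section. Protocol 7.6.5 asks for a pretreatment versus post-treatment comparison of hepatosplenomegaly. It makes normative comparison of certain variables optional, and Protocol 7.6 describes its text as a guide. The comparison of organ volume with normal values depends on such values being available. This stands as a limit: on liver and spleen the SAP has left out a conditional comparison, not broken a firm commitment. It does not remove the analytical problem, because the one summary that remains cannot be read apart from growth. Even a conditional comparison needs the SAP to name the reference or say that none is usable.

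It can also be said that raw and derived data will appear in listings or graphs (SAP 8.1), so values could be rescaled later. That limits the harm. But a reference chosen after open-label data have been seen is not prespecified, and SAP 3.3 allows analyses at any time.

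Three stronger readings are tempting and should not be drawn.

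- *That the SAP replaced the ventricular mass z-score with raw mass.* It did not; it leaves the scale open. SAP 4.3 shortens other protocol entries too, for example leaving out the named bone markers, so abbreviation is a plausible explanation. The protocol's instruction, "scored as a z-score relative to normal ventricular mass", still stands.
- *That SAP 9 is wrong.* It disclaims only major changes, and it is written against Amendment 1, whose body is not supplied. The Amendment 2 summary of major changes lists none to these measures. The wording was therefore probably the same in Amendment 1, but that is an inference.
- *That the liver decreases in Protocol Table 5.2.1 show how much would be masked.* They come from other diseases and are not stated to be relative to normal for age.

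**Conclusion.** The point holds for liver and spleen. As written, SAP 8.7.2 gives a change from baseline that mixes normal growth with drug effect in growing children without a control arm, and it tends to understate a fall relative to normal. That direction assumes only that the normal value rises over follow-up. The amount cannot be obtained from the documents; the grid above shows the mechanism and does not estimate its size.

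For ventricular mass the point is one of wording: the protocol's scale should be restated.

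Severity is minor. These are descriptive secondary and tertiary summaries in about 15 subjects, and neither the primary uGAG analysis nor any error rate or sample size is affected.

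**What to change.** **SAP 4.2 and 8.7.2.** Keep the raw change from baseline. Add, for ultrasound volumes only, a by-visit summary of volume relative to normal for age and sex, with the reference named. Physical-exam findings are qualitative and cannot enter this summary. State beside it that slow organ growth from short stature can look like benefit on an age-normed scale.

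**If no usable reference exists.** Say so in SAP 9 and use a body-size-adjusted volume instead. A length-based adjuster is preferable to weight, which edema or ascites distorts. Protocol 7.5.2.2.1 allows standing height, recumbent length or sitting height, so the SAP should require the same measure throughout for each subject.

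**SAP 4.3 and 8.7.3.** State that ventricular mass is summarised as the z-score the protocol specifies, and name the reference.

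**Cost.** SAP text and derivations only. Ultrasound, echocardiogram, height or length, and weight are already collected, and anthropometrics are scheduled at each Treatment Period ultrasound visit and every 12 weeks afterwards. No new visits or procedures are needed. The one uncertainty is whether a suitable organ-volume reference can be found for this age range.
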